## 7.3 Blinding and Randomization

This is an open label study, and no blinding is required.

Qualifying subjects will be centrally randomized into one of two study groups using a 1:1 randomization list provided by Haleon Biostatistics. Subjects will be randomized into one of two study groups. Study Group 1 will take only the daytime Robitussin product and group 2 will take both the daytime and the nighttime Robitussin products. Before the study is initiated, training and directions for the randomization will be provided to the investigator study team. Study products will be dispensed in sequential order as per the randomization schedule. Only subjects who meet the study inclusion criteria will be randomized to a study product.

## 7.4 Breaking the Blind

Not applicable.

[figure not shown]
# 8 STATISTICAL CONSIDERATIONS AND DATA ANALYSES

## 8.1 Sample Size Determination

Sufficient individuals (approximately 372) will be screened to enroll approximately 260 eligible subjects assuming an estimated 23% drop out rate. It is believed that for this study, 200

completed subjects (100 per treatment group) are deemed sufficient to observe an improvement in the WURSS-21.

## **8.2 Populations for Analysis**

### **8.2.1 Definitions of Analysis Populations**

The following four study populations will be used for statistical analysis:

- The enrolled population will include all subjects who meet the inclusion/exclusion criteria.
- The safety population will include all subjects who use study product at least once. The safety population will be used for analysis of the safety variables.
- The modified Intent-To-Treat (mITT) population will include all subjects who use study product at least once and have data from at least one post baseline QoL questionnaire to support at least one of the primary endpoint assessments. QoL and ePRO data will be summarized using the mITT population only.
- For the Exploratory Endpoint, the Non-Common-Cold-Med (NCCM) population will include all patients in the mITT population who have not used other medicinal products which might influence reported symptom severity. Reported concurrent medications will be assessed in a Blind Data Review (BDR) meeting to identify potentially interfering medications.

## **8.3 Statistical Analyses**

Additional details of the proposed statistical analysis will be documented in the statistical analysis plan (SAP), which will be written following finalization of the protocol and prior to study data analysis. All analyses will be carried out and reported without adjusting for multiple comparisons, reporting nominal p-values.

Each of the treatment groups will be analyzed separately for all endpoints; there is no comparison between the study groups (daytime product only and daytime/nighttime product combination).

Baseline WURSS-21 and the Specific QoL questions are completed at the Virtual Visit, prior to study product(s) shipment to the subject.

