## 2 STUDY OBJECTIVES AND ENDPOINTS

**Table 2-1 Study Objectives and Endpoints**

Each of the treatment groups will be analyzed separately; there is no comparison between the study groups (daytime product only and daytime/nighttime product combination).

Objectives	Endpoints
Primary	
To evaluate the over-time effects of Robitussin on QoL factors and common cold symptoms among individuals experiencing cough associated with common cold, following up to 8 days of treatment using WURSS-21.	Score change from Baseline to each treatment day in: 
 
• WURSS-21 total score
 
• WURSS-21 total symptom domain score
 
• WURSS-21 total QoL domain score
 
• Each of the WURSS-21 symptom scores (10 items in total)
 
• Each of the WURSS-21 QoL scores (9 items in total)
 

Secondary	
To evaluate the over-time effects of Robitussin on QoL factors among individuals experiencing cough associated with common cold, following up to 8 days of treatment, using specific QoL questions.	Score change from Baseline to each treatment day in: 
 
• social activities
 
• feeling self-conscious around people
 
• coughing in public
 
• falling asleep
 
• sleeping through the night
 
• energy
 
• motivation
 

To evaluate the over-time effects of Robitussin on specific QoL questions among individuals experiencing cough associated with common cold, following up to 8 days of treatment, using categorized QoL factors.	Score change from Baseline to each treatment day in: 
 
• Sleep quality
 
• Vitality
 
• Physical activities
 
• Social activities
 

Safety	
To record adverse events (AEs) during study period	Number and percent of patients reporting AEs or serious AEs (SAEs) while on treatment: 
 
• Related to product
 
• Not related to product
 

Exploratory	
Subgroup analysis for primary and secondary endpoints	Subgroups: 
 
• Excluding subjects who took concomitant medications that are known to have an impact on common cold symptoms
 

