*f* WURSS–21 to be completed at the time of Baseline/Screening to confirm eligibility as well as daily during treatment (from Day 1 up to Day 7).

*g* Study product (Robitussin) to be shipped only after screening/baseline assessments are completed and eligibility is confirmed; up to 8 days' worth of study product(s) will be shipped together to ensure there is no interruption in study timeline or treatment duration.

*h* Participant will complete an eDiary documenting Robitussin use each day directly through the Citrus ePRO module.

*i* Participant-reported End of Study Survey will be completed at the end of study directly through the Citrus ePRO module. Participants ending product use early will complete the survey one day after their last reported dose; participants dosing on Day 7 will complete the survey on Day 7.

*j* Participant-reported Change in Health will be recorded two days after last study product administration.

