### **5.4.2 Baseline Assessments**

#### **5.4.2.1 Baseline WURSS-21**

After photo ID verification, the study team will trigger the Baseline WURSS-21 (in appendix section 14.3) for subject self-completion. The purpose of this assessment is to ensure potential participants meet the Inclusion criteria related to the WURSS-21 Symptom domain [minimum score of 5 (moderate) for cough associated with common cold symptoms and at least one other symptom of common cold (at least mild score of 3)]. The study team will review responses as related to determining subject eligibility.

This administration of the WURSS-21 at the Virtual Visit also develops the Baseline for eligible subjects.

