## 6.1 Outcome Assessments

Assessments will be performed by delegated staff at the times, and in the order, defined in the Study Procedures section of this protocol.

The primary objective of the study is to evaluate the over-time effects of two Robitussin Maximum Strength products on QoL factors and common cold symptoms among individuals experiencing cough associated with common cold, following up to 8 days of treatment using WURSS-21.

Links will be sent to the subject daily for self-completion of the following quality of life tools from receipt of product to study conclusion.

- WURSS-21 Questionnaire (in appendix section [14.3](#))
- Additional QoL Questions (in appendix section [14.3](#))

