3.1 Baseline Definition

For all endpoints the baseline value will be self-completed during the screening and enrolment phase. It will, at a minimum, be the latest pre-treatment scores available for the participant.

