4.5 Analysis

4.5.1 Primary Endpoint

4.5.1.1 Primary Endpoint Definition

The primary endpoint will be measured using the Wisconsin Upper Respiratory Symptom Survey (WURSS); 21 question daily symptom report.

WURSS-21 scores will be reported as:

- Total score: sum of questions 2 through to 20
- Total symptoms domains score: sum of the items (questions 2 – 11) in the symptom section (10 individual items on cold symptoms answered on a 0 (does not have this symptom) - 7 (severe scale))
- Total QoL domain score: sum of the domains (questions 12 – 20) in the QoL section (9 individual items on cold interference to QoL answered on a 0 (not at all) - 7 (severely scale))
- Individual symptom item score (10 items)
- Individual QoL item score (9 items)

Change from baseline (Day 0) will be calculated for each subject by subtracting the baseline score from scores at subsequent treatment timepoints (Days 1-7 after baseline) regardless of study product use compliance as long as they have used it at least once and at end of treatment (defined as the last day of study product use or day 7 – whatever event comes first). The percentage improvement will be calculated at each timepoint (Days 1-7, and end of treatment), any timepoints after Day 7 will not be included in the analysis tables but will be included in the subject listings. Results will be presented for both the mITT and NCCM populations in:

- Tables 14.2.1.1.1 through 14.2.1.5.2
- Figures 14.2.3.1 through 14.2.6.2

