4.9 Analysis of Safety

4.9.1 Adverse Events and Serious Adverse Events

All AEs will be coded using MedDRA. AEs will be categorized as related or unrelated by Lindus Health prior to database lock. The number of AEs/SAEs and the number of subjects with AEs/SAEs will be listed and tabulated.

The absolute and relative frequency of adverse events (AEs) in each group will be reported, including the total number of events, the total number of patients experiencing at least one event, and the frequency of events by severity and AE category. Safety analyses will be performed on the Safety population, according to investigational product received. AEs will be regarded as 'treatment emergent' if they occur on or after the first use of investigational product at baseline (Day 0, pre-randomization). In the event of a missing start date, an AE will be assumed to be 'treatment emergent' unless the end date is prior to starting treatment. In case of misallocation compared to the randomization schedule, TEAEs will be associated with the most recent investigational product received.

A listing of all Treatment Emergent AEs (TEAEs) will be presented for all subjects in the Safety population with the following AE summaries (number of distinct AEs and frequency/proportion of subjects affected) presented by treatment group and overall:

- TEAEs—Overview (Table 14.3.1.1)
- TEAEs by System Organ Class (SOC) and Preferred Term (PT) (Table 14.3.1.2)
- TEAE by Relationship, System Organ Class and Preferred Term (Table 14.3.1.3)
- TEAE by System Organ Class, Preferred Term and Worst Severity (Table 14.3.1.4)
- Treatment Emergent Serious Adverse Events by System Organ Class and Preferred Term (Table 14.3.1.5)

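### Baseline is scored before the product ships and doubles as the entry score, and the day count has no single anchor, so change scores can include untreated days and regression to the mean

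*Protocol*

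**What the plan says.** **Baseline and shipping.** Protocol 8.3: "Baseline WURSS-21 and the Specific QoL questions are completed at the Virtual Visit, prior to study product(s) shipment to the subject". A footnote to Protocol Table 5-1 says that product is "to be shipped only after screening/baseline assessments are completed and eligibility is confirmed". Under Protocol 7.2 the order is placed after randomization. Protocol 5.4.5 has the subject confirm receipt in an online questionnaire and provides for a replacement if the parcel is lost or damaged. No section sets a maximum delivery time. Table 5-1 note a mentions same-day receipt as a condition for a same-day sequence, not as a requirement.

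**Day count.** The Protocol Table 2-1 endpoint is "Score change from Baseline to each treatment day in" the listed scores. Protocol 6.1 sends the daily links "from receipt of product to study conclusion". SAP 4.5.1.1 computes change for "scores at subsequent treatment timepoints (Days 1-7 after baseline"), with baseline as Day 0. Protocol Table 5-1 and section 5.6 place product use on Day 0 to Day 7.

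**Entry score and baseline.** Inclusion criterion 4 requires a WURSS-21 cough score of at least 5 and one other symptom at 3 or more. Protocol 5.4.2.1 adds: "This administration of the WURSS-21 at the Virtual Visit also develops the Baseline for eligible subjects". SAP 3.1 wants the baseline to "be the latest pre-treatment scores available for the participant", but only one pre-treatment administration is scheduled.

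**Safety.** SAP 4.9.1 calls an event treatment-emergent if it occurs "on or after the first use of investigational product at baseline (Day 0, pre-randomization").

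**Acknowledged limits.** Protocol 3.2 names natural resolution and concomitant medication. It mentions neither delivery delay nor regression to the mean.

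**The concern.** The analysis is a within-group change from baseline with no comparison between groups (Protocol 8.3). Anything that moves scores between the virtual visit and a later form therefore stays in the estimate, and nothing cancels it.

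Three things follow:

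- If product arrives late, a score labelled as a treatment day may describe a subject who has not yet been treated. The mITT definitions (Protocol 8.2.1, SAP 4.2.3) require one use of product and one post-baseline form, but not that the form come after the dose.
- The score that admits a subject is high partly by chance, so the next score tends to be lower with no treatment and no recovery. The cough item is most exposed. It is a primary endpoint and the only individual symptom chosen for topline output (SAP Appendix 1).
- Adverse events are collected from randomization (Protocol 9.3). If Day 0 is programmed as the start of treatment, events between randomization and first dose would be tabulated as treatment-emergent.

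**Working it through.** **1. The plan's own figures.** 200 / (1 − 0.23) = 259.7, so the 260 enrolled reproduces. 260 / 372 = 0.70, so the plan expects about 70% of those screened to meet all criteria. The share meeting the cough criterion alone must be at least that.

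**2. The day clocks side by side.** Suppose product arrives L days after the virtual visit. The documents give no L, so 0 to 3 is assumed.

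- Counting from baseline (SAP 4.5.1.1), up to L of the seven daily scores can precede any dose, and the untreated share of the Day 7 interval is L/7.
- Counting from receipt (Protocol 6.1), the daily forms follow receipt, but the baseline is L days old and the untreated share is L/(7 + L).

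| L (days) | From baseline | From receipt |
|---|---|---|
| 0 | 0% | 0% |
| 1 | 14% | 12% |
| 2 | 29% | 22% |
| 3 | 43% | 30% |

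The clocks agree only at L = 0.

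**3. Direction of the delay bias.** Cough began at most 48 hours before the visit (inclusion criterion 3). Protocol 1.2 puts the peak of cold symptoms at 1 to 3 days after they appear. With L of 1 to 3 days, first dose falls up to 3 to 5 days after cough onset. The untreated interval can therefore span a rise, the peak or a decline, and its sign is not fixed.

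**4. Regression to the mean on the cough item.** Assumed: an observed score with given mean and SD, test-retest correlation r, no drug effect and no natural course. Selection at 5 or more on a rounded scale corresponds to a cut at 4.5. The expected fall is

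(1 − r) × SD × φ(k) / (1 − Φ(k)), with k = (4.5 − mean) / SD.

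Example with 70% passing: mean 5.29, SD 1.5, r 0.7 gives k = −0.527 and 0.3 × 1.5 × 0.347 / 0.701 = 0.22. Simulation on the rounded 0–7 scale gives 0.25, because rounding adds a little error. Simulated results, with z = mean change / SD of change × √100:

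| Mean, SD | Passing cough ≥5 | Fall, r 0.8 to 0.6 | z at n = 100 |
|---|---|---|---|
| 5.5, 1.5 | 75% | 0.15 to 0.28 | 1.7 to 2.5 |
| 5.29, 1.5 | 70% | 0.18 to 0.33 | 2.0 to 2.8 |
| 5.0, 1.0 | 69% | 0.15 to 0.25 | 2.0 to 2.7 |
| 5.0, 1.5 | 63% | 0.21 to 0.39 | 2.3 to 3.3 |
| 4.0, 1.5 | 37% | 0.36 to 0.67 | 3.8 to 5.4 |

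The first three rows are near the plan's screening ratio. There the chance of a nominal two-sided p < 0.05 with no effect at all, Φ(z − 1.96), is about 41% to 81%. Holding 70% passing and widening to SD 1.0–2.0 and r 0.5–0.9 gives a fall of 0.09 to 0.49 points and a chance of 30% to 94%. For scale, n = 100 detects a standardized change of (1.96 + 0.84) / 10 = 0.28 with 80% power.

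**5. Total score.** Assumed: 19 items with SD 1.5, a mean of 4.0 for cough and 3.5 for the others, r 0.5–0.9, and 0 to 50% of the error shared across items. The fall is 0.2 to 7.8 points, or 0.07 to 0.41 standardized. The cough item at the same mean, SD and r values falls 0.28 to 0.61 standardized, so the total is less affected at each r.

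**6. Treatment-emergent rule.** First use needs product, product is ordered after randomization (Protocol 7.2), so first use cannot be pre-randomization. The parenthetical is wrong whatever the delivery time.

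**The case against.** The strongest reply is that the plan intends same-day use. Same-day receipt is foreseen, product use and the eDiary are marked on Day 0, Protocol 6.1 sends daily links only once product has arrived, and the post-treatment QoL items are worded as after use. On that reading no daily form precedes product. This stands as far as it goes. A reader might infer that Day 1–7 changes do contain untreated days, but the documents do not show that; they only fail to exclude it. Even under Protocol 6.1, any delay leaves an untreated gap between baseline and receipt.

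A reader might also infer that delay flatters the product through natural decline. Step 3 shows why that does not follow.

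A third tempting reading is that regression to the mean inflates every estimate to a similar degree. Selection by score uses cough and one other symptom. The QoL items are not score-selected, although one disrupted night is required. The larger cough figures also need inputs under which only 37% pass the cough criterion, which does not fit 260 of 372.

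On safety, the operative words of SAP 4.9.1, onset at or after first use, are sound; only the parenthetical fails.

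Finally, natural resolution is the main confounder, is already acknowledged, and would survive any new baseline. That is true, but it does not excuse two avoidable and unacknowledged sources of bias. The baseline covariate in the mixed model does not remove either from a within-group change.

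**Conclusion.** The point holds in a limited form. Baseline precedes shipping, no delivery window or later pre-dose form is scheduled, and the documents use day clocks that agree only with same-day delivery. Change scores can therefore include untreated days. If days count from baseline, a treatment-day score can be pre-dose and a pre-dose form could qualify a subject for mITT. How often this happens, and which way it biases, cannot be told from the documents.

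Reusing the entry score as baseline adds regression to the mean whatever the delivery time. For the cough item this is about 0.15 to 0.3 points, z about 1.7 to 2.8 at 100 per group, near the plan's screening ratio. It reaches about 0.7 points (z 5.4) under less favourable inputs and is smaller for totals and QoL items. Mean, SD, r and lag are all assumptions. The pre-randomization wording in SAP 4.9.1 is an error on the documents' own terms.

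**What to change.** For all subjects, in the SAP:

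- Use one anchor: count Day n from the first dose recorded in the eDiary, and reconcile Protocol 6.1 with SAP 4.5.1.1.
- Require the mITT post-baseline form to follow the first dose, and drop pre-dose forms from the post-baseline data. The eDiary items listed in Protocol 5.5 do not include a dose time, so state a rule for forms completed on the date of first dose.
- Delete the parenthetical in SAP 4.9.1, so that treatment-emergent means onset on or after the recorded first dose.
- Report the distribution of the lag from baseline to first dose, and show results for subjects dosed on the day of the virtual visit.
- Name regression to the mean as a limitation beside natural resolution.

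These steps need SAP wording and dates from the eDiary and receipt confirmation. SAP section 5 shows that data collection had already begun, so they are the only remedy for subjects already enrolled.

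For subjects not yet enrolled, amend Protocol 5.4.2.1, 5.4.2.2 and 8.3. Add the WURSS-21 and the specific QoL questions to the receipt-confirmation questionnaire, completed before the first dose. Use them as baseline, which SAP 3.1 already allows, and keep the virtual-visit score for eligibility only.

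The cost is a protocol amendment, a few minutes per subject, and a somewhat smaller change from baseline. In the simulation this brings the regression on cough to about zero if errors on the two occasions are independent. With same-day receipt the 24-hour recall periods overlap, so errors would be correlated and some regression would remain. Natural resolution stays in the estimate.

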### **8.3.1 Exclusion of Data from Analysis**

Exclusion of any data from the analyses will be determined during a BDR meeting prior to database lock. Any reasons for exclusion from an analysis population will be listed, if applicable.

### 8.3.2 Primary Endpoint Analysis(es)

For the primary objective, measurements of health related QoL indicators and cold symptoms will be evaluated using daily WURSS-21 scores (total scores, total QoL domains scores, total symptom domains scores, and single symptom and QoL domains scores) change from baseline to each treatment day to determine the effectiveness of the two treatment groups (Daytime, Daytime+Nighttime).

Change from Baseline in mean WURSS-21 scores to each treatment day will be summarized and analyzed using a mixed-effects model for repeated measures (MMRM) with treatment, treatment day as a discrete variable, and applicable baseline WURSS-21 scores as fixed effect and a random intercept for each subject. Estimated marginal mean differences between baseline and each treatment day will be reported by treatment group including the mean difference on the original scale, standardized effect size including 95% confidence intervals (CI), and the respective p-value. The distribution of each outcome is assessed using Q-Q-plots by treatment group. In case of apparent deviations from the normal distribution, the changes from baseline are assessed using a Wilcoxon signed-rank test.

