### 3.2 Scientific Rationale for Study Design

RWE studies reflect product use in everyday life. They offer the opportunity to gather information on currently marketed products to not only substantiate clinical evidence, but to gather information on participant quality of life from the target patient population.

The Wisconsin Upper Respiratory Symptom Survey (WURSS) is an evaluative illness-specific quality of life instrument, designed to assess daily the negative impact of acute upper respiratory infection, presumed viral (the common cold). WURSS-21 is the short version of this validated instrument. WURSS-21 includes a single question on a global severity score, a symptoms domain (10 items), a functional domain (9 items) and an overall question on improvement/deterioration since yesterday. While the WURSS-44 covers more symptoms, the WURSS-21 exhibits similar performance in terms of reliability, responsiveness, importance-to-patients, and convergence with other measures.

Subjects with cough associated with common cold, who seek to treat with study treatment (Robitussin) will complete WURSS-21 and a specific QoL questionnaire once per day. Study treatment use will be reported via electronic diaries (eDiary). These measures will provide information on the effects of Robitussin over the natural course of their cough associated with common cold. This supports evaluation of the daily effects that may be attributable to the study treatment.

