#### Limitations of the study

Given the natural course of the common cold, data collected during this study may be confounded by the natural resolution of the disease. Within 24 hours of cold onset, most patients report an escalation in the number of symptoms they experience, including sore throat, nasal congestion, runny nose, and headache. Over the initial days of having a cold, sore throat appears to be most bothersome on day 1 followed by nasal congestion and then cough.

Given the natural course of the disease, making sure subjects have access to treatment when cough symptoms are at their peak will allow for subsequent QoL data capture, reducing the influence of confounding variables.

There is substantial evidence to show that different symptoms of common cold overlap during the natural course of the disease. Subjects may likely be using over-the-counter antipyretics/analgesics for fever and/or headache, which may influence their overall QoL and confound data collected. During this study patients will be prompted to report medications they take for symptom relief, along with any changes in medication over the course of their study participation, which will allow the study team to review collected data objectively. Subjects who report taking medication(s) known to have an impact on common cold symptoms will be excluded for subgroup analysis.

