4.6 Analysis of Secondary Objectives

4.6.1 Secondary Endpoint: Specific QoL Scores

Measurements of health related QoL indicators will be evaluated using the specific QoL scores and categorized QoL scores change from baseline to each treatment day to determine the effectiveness of the two treatment groups (Daytime, Daytime+Nighttime).

The Specific QoL Scores consist of 7 separate questions on QoL, scored 0 ('not at all') to 7 ('severely'). Lower scores represent better outcomes. Each specific question covers one of the following topics:

- Social activities
- Feeling self-conscious around people
- Coughing in public
- Falling asleep
- Sleeping through the night
- Energy
- Motivation

Changes from baseline in Quality of Life (QoL) domain scores (Sleep Quality, Social Activities, Physical Activities, and Vitality) will be analyzed longitudinally using the same methodological approach as the primary outcome. The analysis will be conducted for the mITT population, with results presented in Tables 14.2.2.1.(1-2) and Figures 14.2.4.(1-2); 14.2.5.(1-2). A linear mixed-effects model for repeated measures (MMRM) will be fitted separately for each QoL domain. Each model will include treatment day as a categorical fixed effect, baseline QoL score as a continuous covariate, and a random intercept for subject to account for within-subject correlation. The models will employ an unstructured covariance matrix, Kenward-Rogers degrees of freedom adjustment, and restricted maximum likelihood estimation (REML) to ensure valid inference. For each QoL domain and treatment group, the following estimates will be reported at each timepoint: estimated mean changes from baseline with 95% confidence intervals, between-treatment differences in mean changes with 95% confidence intervals, standardized effect sizes (Cohen's d) with 95% confidence intervals, and associated p-values for treatment comparisons. Statistical significance will be evaluated at $\alpha=0.05$ level. Given the exploratory nature of the QoL analyses, p-values will be reported without adjustment for multiplicity, but interpretations will consider the potential impact of multiple testing on Type I error rates. Sensitivity analyses for the robustness of results to missing data and distributional assumptions will follow the same approach as specified for the primary outcome.

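### Within-group tests of zero change cannot determine effectiveness: there is no untreated arm, and scores are expected to fall without any product effect

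*Protocol*

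**What the plan says.** - **Purpose and test.** Protocol 8.3.2 evaluates the daily WURSS-21 scores as "change from baseline to each treatment day to determine the effectiveness of the two treatment groups". It adds: "Estimated marginal mean differences between baseline and each treatment day will be reported by treatment group", with confidence intervals and p-values. Protocol 8.3.3 does the same for the secondary scores. SAP 4.5.1.2 evaluates the primary endpoints at the 5% level. SAP 4.6.1 and 4.6.2 repeat the purpose: "to determine the effectiveness of the two treatment groups (Daytime, Daytime+Nighttime)".
- **Comparator.** Protocol 3.1 describes two active arms and no untreated or placebo arm. Protocol 8.3 says: "Each of the treatment groups will be analyzed separately for all endpoints; there is no comparison between the study groups". SAP 1.2 repeats this rule. SAP 4.6.1 and 4.6.2 nevertheless specify p-values for between-treatment comparisons.
- **Entry and baseline.** Protocol 4.3 requires cough onset within 48 hours and a WURSS-21 cough score of at least 5. Protocol 5.4.2.1 says: "This administration of the WURSS-21 at the Virtual Visit also develops the Baseline for eligible subjects".
- **Natural course.** Protocol 1.2 puts the symptom peak at 1 to 3 days, with symptoms then usually lasting 3 to 10 days. Follow-up covers Days 1 to 7.
- **Limitation.** Protocol 3.2 concedes that "data collected during this study may be confounded by the natural resolution of the disease". It then says that access to treatment at the cough peak "will allow for subsequent QoL data capture, reducing the influence of confounding variables". Of the daily measures it says: "This supports evaluation of the daily effects that may be attributable to the study treatment".

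**The concern.** A p-value against zero change answers whether scores moved. It says nothing about why. In a self-limiting illness that is measured from near its worst point, scores are expected to fall in people who take nothing. A significant fall is therefore no evidence that a syrup worked, yet the plan says that this result will determine effectiveness. Protocol 1.1 and SAP 1 also give supporting the effectiveness of the products as the reason for the study. At stake is whether the stated primary conclusion can follow from the primary analysis at all.

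**Working it through.** **1. Group size.** Protocol 8.1: 200 completers / (1 − 0.23) = 259.7, so 260 enrolled, or 100 completers per group. This reproduces. (Protocol 4.1 assumes 30% dropout, which leaves 260 × 0.70 = 182.) The 200 itself cannot be derived, because no effect size, SD or power is given.

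**2. What it takes to reject zero change.** A paired t-test stands in for the day-specific model estimate, two-sided at 5% (sidedness is not stated). The noncentrality is d√n, where d is the mean change divided by the SD of change. With n = 100:

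- d = 0.28: 80% rejection
- d = 0.4 (noncentrality 4.0): 97.7%
- d = 0.5 (noncentrality 5.0): 99.9%

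Subjects who stop early leave fewer reports on later days. With n = 70, d = 0.5 still gives 98.5%.

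**3. Natural recovery with no product effect.** The documents give no mean or SD, so I assume a baseline total of 50 to 70 and an SD of change of 15 to 30.

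- 5% recovery (2.5 to 3.5 points): 13% to 64% rejection
- 10% recovery (5 to 7 points): 38% to 99.6%
- 20% recovery (10 to 14 points, d = 0.33 to 0.93): 91% to 100%

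**4. Regression to the mean on the cough item, with no recovery and no product effect.** Expected drop = (1 − ρ) × SD × φ(a)/(1 − Φ(a)), with a = (4.5 − μ)/SD. Assumed: μ 3.5 to 5.0 before selection, SD 1.5, day-to-day correlation ρ 0.5 to 0.9.

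- Largest: μ = 3.5, ρ = 0.5, a = 0.67. Drop = 0.5 × 1.5 × 1.265 = 0.95 points.
- Smallest: μ = 5.0, ρ = 0.9, a = −0.33. Drop = 0.1 × 1.5 × 0.60 = 0.09 points.

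Simulating scores rounded to 0–7 and selected at 5 or more gives drops of 1.02 and 0.12 points. Rejection at n = 100 is:

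| μ | ρ = 0.5 | ρ = 0.7 | ρ = 0.9 |
|---|---|---|---|
| 3.5 | 100% | 100% | 93% |
| 4.5 | 99.9% | 96% | 61–63% |
| 5.0 | 96–97% | 82% | about 41% |

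**5. Carry-over to the total.** If day-to-day noise is specific to each item, a cough drop of 0.3 to 1.0 points moves the 19-item total by the same 0.3 to 1.0 points. With an SD of change of 15 to 30, d is 0.01 to 0.07 and rejection is 5% to 10%, close to nominal. Noise shared across items would raise this. The documents do not say which applies.

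**6. The peak argument.** Protocol 3.2 treats access at the peak as reducing confounding. The expected untreated change is the later level minus the baseline level. Taking the baseline at the peak makes that difference as large as it can be, so the argument runs the wrong way.

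**The case against.** The strongest reply is that the study is openly uncontrolled. It names natural resolution as a limitation, frames its objective as effects over time, and hedges attribution with the word may. SAP 4.5.1 does not use the effectiveness wording for the primary endpoint. All of that is true. But the disclosure changes nothing in the analysis: the only analytic response in Protocol 3.2 is the subgroup without other cold medicines, which addresses neither recovery nor regression to the mean. SAP 4.5.1.2 keeps the same tests.

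Four stronger readings are tempting, and the documents do not support them.

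- *Every test is near certain to be significant.* Entry is within 48 hours of cough onset, so Days 1 and 2 may precede the peak and show little change or worsening. Protocol 1.1 also reports cough lasting more than 6 days in 35.2%. The point is strong for later days.
- *The entry rule inflates all the primary scores.* The threshold of 5 applies to cough alone. The effect on the totals could be negligible (step 5). The second-symptom and disrupted-sleep criteria may add selection, but this was not modelled.
- *The plan contains no between-group contrast.* That holds for the primary endpoint only. SAP 4.6.1 and 4.6.2 specify such contrasts for secondary scores. They contradict Protocol 8.3 and SAP 1.2. Because both arms are active, they could not show an effect against no treatment anyway.
- *The design is invalid without a control arm.* An uncontrolled study can validly describe change during use. What it cannot support is the effectiveness conclusion.

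**Conclusion.** The plan is wrong as written on this point: the stated conclusion does not follow from the analysis, whatever the results. That rests on the text and needs no assumption. The size does rest on assumptions. Under no product effect, a natural change of 0.4 to 0.5 SD rejects zero change 98% to 99.9% of the time at 100 per group. Regression to the mean alone rejects about 41% to 100% of the time for the cough item over the assumed range, against a nominal 5%. The means, SDs, correlations and recovery fractions are mine; the documents give none. Regression to the mean on the total scores remains an open question.

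**What to change.** 1. In Protocol 8.3.2 and 8.3.3 and SAP 4.6.1 and 4.6.2, replace the stated purpose of determining effectiveness with: to describe change during use of the two regimens.
2. Bring the effectiveness statements in Protocol 1.1 and SAP 1, and the power statement in Protocol 4.2, into line with that purpose.
3. In Protocol 3.2, delete the sentence ending "will allow for subsequent QoL data capture, reducing the influence of confounding variables" and the sentence "This supports evaluation of the daily effects that may be attributable to the study treatment".
4. State in SAP 4.5.1.2 and 4.6 that within-group estimates, confidence intervals and any p-values include natural recovery and, for cough, regression to the mean, and will not be reported as evidence of product effectiveness. Dropping the p-values is optional, because a 95% interval that excludes zero carries the same test.
5. Reconcile the between-group p-values in SAP 4.6.1 and 4.6.2 with Protocol 8.3 and SAP 1.2.

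The cost is wording in both documents and a less favourable claim. No patients, data collection or control arm are added.
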